Assessment of Continuous Positive Airway Pressure Therapy in OSA and ILD

ClinicalTrials.gov ID: **NCT03901534**

Date of IRB approval: **June 3, 2024**

BACKGROUND

Study Purpose and Rationale

Idiopathic pulmonary fibrosis (IPF) is a progressive fibrotic disease of the peripheral lung parenchyma that affects 0.5% of older adults in the U.S. and confers a median survival of only 3.8 years.¹⁻³ While pirfenidone and nintedanib slow disease progression, neither drug reverses fibrosis nor prevents ongoing subclinical alveolar epithelial cell (AEC) injury, the antecedent cause of fibrosis in IPF.^{4,5} We and others have shown that subclinical AEC injury as well as extracellular matrix (ECM) remodeling are also detectable using serum biomarkers, including increases in surfactant protein-D (SP-D), Krebs von den Lungen-6 (KL-6), and MMP-7 (a marker of AEC injury and ECM remodeling). Each of these biomarkers is also elevated in IPF and other fibrotic ILDs.⁶⁻¹¹ We and others have found that obstructive sleep apnea (OSA), a condition that is highly prevalent in adults with fibrotic interstitial lung diseases, including IPF, is also associated with increases in serum KL-6, SP-A and MMP-7, and with angiopoietin-2 (Ang-2; an endothelial marker), and that OSA is associated with subclinical ILD on CT.¹²⁻¹⁵ These data support (1) the use of serum biomarkers to detect subclinical AEC injury and ECM remodeling, and (2) the hypothesis that OSA may contribute to subclinical AEC injury. Based on these data, our central hypothesis is that moderate-to-severe obstructive sleep apnea causes subclinical AEC injury and, in susceptible individuals, peripheral lung fibrosis and fibrotic ILD.¹⁶ OSA might lead to AEC injury and ECM remodeling by exerting peripheral stretch of the lung, which has been hypothesized to be an underlying cause of IPF and other fibrotic ILDs.^{12,13} Obstructive apneas and hypopneas are characterized by repetitive forceful inspiratory efforts against a completely or partially closed airway.¹⁷ This causes wide swings in pleural pressure exerting peripheral tractional stress on the lung, potentially causing stretch and injury to AECs analogous to that which occurs during positive pressure ventilation.¹⁸⁻²⁰ Other mechanisms linking OSA and subclinical AEC injury are possible, including promotion of oxidative injury by intermittent hypoxia and microaspiration from gastroesophageal reflux disease (GERD).^{21,22} We propose to leverage the Multi-Ethnic Study of Atherosclerosis (MESA) Sleep Study, a community-based cross-sectional study, the HeartBEAT and BestAIR randomized clinical trials of CPAP for OSA, and an inception cohort of ILD patients diagnosed with OSA. We propose to establish OSA as a modifiable contributor to AEC and endothelial injury and thereby provide

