
sufficient evidence to support a large-scale clinical trial testing whether CPAP improves clinical outcomes in IPF. This will be achieved through three Specific Aims:

Specific Aim 1: Determine whether greater OSA severity is associated with higher levels of serum biomarkers of AEC and endothelial injury and ECM remodeling in community dwelling adults.

Specific Aim 2: Determine whether CPAP use is associated with reductions in AEC and endothelial injury and ECM remodeling biomarkers in adults with moderate-to-severe OSA. Using stored serum samples from the HeartBEAT and BestAIR trials, we will assess serum MMP-7, SP-D, SP-A, and Ang-2 levels in adults with moderate-to-severe OSA after randomly allocated CPAP or no-CPAP. We hypothesized that CPAP use will be associated with reductions in these biomarkers. This hypothesis has been proven incorrect. Contrary to our hypothesis, the levels of four biomarkers of lung inflammation and extracellular remodeling were not reduced by CPAP in patients with OSA. Indeed, CPAP therapy was associated with an increased circulating level of Ang-2, an endothelial growth factor that is released from pulmonary endothelial cells in the setting of acute lung injury. This finding raises the possibility that CPAP, by increasing alveolar distension, may exacerbate processes that contribute to lung inflammation in OSA.

Original Specific Aim 3: 1) Determine whether untreated OSA promotes AEC and endothelial injury and ECM remodeling biomarkers in adults with ILD and OSA compared with those without OSA; 2) Determine prospectively whether clinically-initiated 4-week PAP therapy increases markers of alveolar endothelial lung injury in OSA.

The results of **Aim 2** analysis indicating potential harm associated with CPAP therapy in OSA necessitated revision of the original aim 3. The **revised Aim 3** is: a) to determine prospectively whether clinically-initiated 4-week PAP therapy increases markers of alveolar endothelial lung injury in OSA; b) to determine whether untreated OSA promotes AEC and endothelial injury and ECM remodeling biomarkers in adults with ILD and OSA compared with those without OSA. Rationale behind revision of Aim 3: Considering that CPAP unexpectedly increased a marker of alveolar endothelial injury in OSA patients without known ILD, we think it is essential to

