validate these findings in a prospective cohort and to document prospectively whether untreated OSA worsens existing lung injury in patients with concomitant ILD. We will use a two-pronged approach to address this question: 1) We plan to recruit prospectively additional 78 patients with untreated moderate-to-severe OSA and assess the above biomarkers of alveolar endothelial injury before and after 4 weeks of clinically-initiated PAP therapy (not randomly allocated owing to the well-recognized societal hazard posed by untreated OSA patients with daytime somnolence). Using the effect size and SD estimates from the HeartBEAT and BestAir samples, a sample of 78 patients will provide 80% power to detect an effect of the size that we observed in **Aim 2** with $\alpha(2) = 0.05$; 2) We will recruit all participants as planned for **Aim 3** (anticipated 100 patients with ILD and concomitant OSA and 65 patients with ILD who do not have OSA) and compare their baseline levels of alveolar epithelial and endothelial injury biomarkers. This approach is crucial to establish whether patients with concomitant ILD and OSA have a greater degree of alveolar endothelial injury compared with ILD patients without OSA. If OSA turns out not to contribute independently to alveolar endothelial injury, this information would also be valuable considering that PAP may worsen existing alveolar endothelial injury in ILD patients, which suggest that alternative treatments for OSA that do not increase alveolar distension (for example, oral appliances) may be particularly suitable for patients with concomitant ILD and OSA. After validating our findings from Aim 2 as described above, we will explore in future studies whether oral appliances lower markers of AEC and endothelial injury in ILD patients with OSA.

Study Design

Aim 1: Determine whether the greater OSA severity is associated with higher levels of serum biomarkers of AEC and endothelial injury and ECM remodeling in community dwelling adults. We will perform cross-sectional analyses in this Aim.

Sampling frame and participants: We will sample participants from the MESA Sleep Study. We will sample the 1,830 MESA Sleep study participants who have available polysomnography data and no self-reported lung disease. We realize that a small proportion of participants will have missing or low-quality samples.

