Selection Criteria, Expected Enrollment, and Screening: This study plans to enroll approximately 165 subjects with interstitial lung disease. We anticipate that 100 of those will have concomitant OSA and 65 will not have concomitant OSA. We will enroll 78 OSA patients from The Columbia University Center for Sleep Medicine and assess the above biomarkers of alveolar endothelial injury before and after 4 weeks of clinically-initiated PAP therapy (not randomly allocated owing to the well-recognized societal hazard posed by untreated OSA patients with daytime somnolence).

Inclusion Criteria for Patients with ILD:

1. Informed consent
2. Age 18 years or greater
3. Diagnosis of any of the following fibrotic interstitial lung diseases as defined by ATS/ERS/JRS/ALAT guidelines and research statements and Delphi surveys^{3, 4, 5}:
Idiopathic pulmonary fibrosis - Idiopathic non-specific interstitial pneumonia (NSIP) with fibrosis - Chronic hypersensitivity pneumonitis with fibrosis - Connective tissue disease related interstitial lung disease (CTD-ILD) - Unclassifiable idiopathic interstitial pneumonia with fibrosis

Exclusion criteria for Patients with ILD:

1. Clinically significant lung disease other than fibrotic interstitial lung disease
2. Planned change to the IPF treatment during the study period
3. Current cigarette smoking (past 4 weeks)

4. Lower respiratory tract infection in past 60 days. (Upper respiratory tract infection is not a contraindication)
5. History of life threatening cardiac arrhythmias
6. Known chronic heart failure (LVEF < 45% or echo evidence of RV dysfunction or PH)
7. Chronic opiate analgesic use
8. History of sleepiness-related automobile accident within past year of enrollment
9. Expected survival time in the opinion of the investigator of less than 6 months
10. History of stroke or spinal cord injury

Study Overview: After informed consent and review of inclusion/exclusion criteria, study participants will undergo full-night polysomnography at their baseline visit (see below).

Phlebotomy, spirometry, 6-minute walk test, diffusing capacity, and questionnaires completed at the research visit.

Inclusion criteria for OSA patients:

1. Age >18 years
2. Clinical diagnosis of untreated OSA documented by nocturnal polysomnography.

Exclusion criteria for OSA patients:

1. Current treatment with CPAP or oral appliance
2. Identical exclusion criteria as for ILD patients

STATISTICAL PROCEDURES

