Outcome measures: 1) Determine whether untreated OSA promotes AEC and endothelial injury and ECM remodeling biomarkers serum (MMP-7, SP-D, osteopontin and Ang-2) in adults with ILD and OSA compared with those without OSA; 2) Determine prospectively whether clinically-initiated 4-week PAP therapy increases markers of alveolar endothelial lung injury (MMP-7, SP-D, osteopontin and Ang-2) in OSA. All assays will be performed in [name] lab as described in Aim 1. Secondary outcomes will include changes in FVC, DLCO, 6-minute walk distance, dyspnea, and HRQOL.

Data Management: We will use a REDCap database for data entry and management as we have previously done in the Lung Transplant Body Composition Study.

STUDY PROCEDURES

For patients with ILD, after informed consent and review of inclusion/exclusion criteria, study participants will undergo home polysomnography (see below). Phlebotomy, spirometry, diffusing capacity and questionnaires will be measured at the research visit.

Participants with ILD will undergo home polysomnography (PSG) after they have consented to the study. We will use the Nox A1 sleep recorder manufactured by Nox Medical (Reykavik, Iceland) for the home PSG recordings. This will strictly be a research study and not meant for clinical purposes. PSG devices will be returned to Columbia and recordings uploaded by the research team. After being uploaded, studies will be exported in standardized format (European Data file; edf) and transferred by secure FTP to the Sleep Reading Center at Brigham & Women's Hospital for scoring by a single research sleep technologist according to well-established protocols. Brigham Sleep Reading Center will perform interpretation using standard AASM scoring criteria.

For patients with OSA only (without ILD), they will undergo clinically indicated polysomnography in the Center for Sleep Medicine. The investigators have no role in determining the need for polysomnography or CPAP therapy in this OSA only cohort. CPAP will be prescribed by their clinician provider and not by the study investigators. Therefore, polysomnography and CPAP are not considered study procedures for OSA only cohort.

Supplemental oxygen: If participants use supplemental oxygen while sleeping at baseline, they will use their supplemental oxygen as prescribed by their healthcare provider during the home PSG.

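### Aim 3a lists four unranked markers as alveolar endothelial although the document classes only Ang-2 as endothelial, so a chance rise in any of them would satisfy the aim as worded

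*Combined protocol and SAP*

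**What the plan says.** Outcome measures, item 2, defines the Aim 3a outcome: "Determine prospectively whether clinically-initiated 4-week PAP therapy increases markers of alveolar endothelial lung injury (MMP-7, SP-D, osteopontin and Ang-2) in OSA". Item 1 of the same paragraph, on the ILD comparison, gives the same four markers a broader label: "promotes AEC and endothelial injury and ECM remodeling biomarkers serum (MMP-7, SP-D, osteopontin and Ang-2) in adults with ILD and OSA". The next tier follows directly: "Secondary outcomes will include changes in FVC, DLCO, 6-minute walk distance, dyspnea, and HRQOL". No marker is called primary.

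The shorter endothelial label for the 78-patient cohort, "assess the above biomarkers of alveolar endothelial injury before and after 4 weeks of clinically-initiated PAP therapy", stands both in Study Purpose and Rationale and in Selection Criteria, Expected Enrollment, and Screening. The aim itself refers to endothelial markers in the plural in Study Purpose and Rationale, in Study Design and in Research Questions/Hypotheses.

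The reason given for revising Aim 3 is singular: "CPAP unexpectedly increased a marker of alveolar endothelial injury in OSA patients without known ILD". The sample-size sentence in the same section says that 78 patients give "80% power to detect an effect of the size that we observed in" Aim 2, at two-sided alpha 0.05. It gives no marker, effect size, SD or test. The text under Statistical Procedures covers study procedures, outcomes and data management, and contains no analysis method for Aim 3a.

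**The concern.** Item 2 groups four proteins under one injury label that, on the document's own classification, fits one of them. It also gives no way to turn four results into one answer.

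Aim 3a is a validation exercise. Aim 2 looked at several markers, expected them to fall, and found Ang-2 raised in the adherent CPAP users. A signal found in that way needs a confirmatory test on a marker fixed in advance. The rationale also makes the next step, oral-appliance studies, follow from that validation.

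As item 2 is worded, flat Ang-2 with a chance rise in osteopontin, SP-D or MMP-7 could be reported as PAP increasing endothelial injury. That would be a statement of harm resting on a marker that the document does not regard as endothelial.

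**Working it through.** **1. Label against the document's own classes**

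| Marker | Class given | Where |
|---|---|---|
| Ang-2 | endothelial: "angiopoietin-2 (Ang-2; an endothelial marker" | Study Purpose and Rationale; Scientific Abstract |
| MMP-7 | epithelial injury and matrix: "MMP-7 (a marker of AEC injury and ECM remodeling" | Study Purpose and Rationale |
| SP-D | alveolar epithelial | Study Design (Aim 2, completed); Scientific Abstract |
| Osteopontin | fibrogenesis and matrix remodeling | Study Design (Aim 2, completed) |

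One of the four fits the item 2 label. All four fit the item 1 label.

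**2. The plan's own figure**

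The 78 cannot be reproduced, because no effect size or SD is given. It can only be solved backwards. Assuming a paired comparison and the normal approximation, d = (1.960 + 0.842)/√78 = 2.802/8.832 = 0.317 (0.321 with a paired t test). This is an implied value and not a figure from the document. Ang-2 is the only reported increase in Aim 2, so it is the evident, though unnamed, basis.

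**3. False increases as the aim is worded**

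Assumptions: no marker truly changes; each is tested two-sided at 0.05; only rises count (2.5% each); a rise in any marker is read as positive; the between-marker correlation ρ is assumed.

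- ρ = 0: 1 − 0.975⁴ = 0.0963.
- ρ > 0: numerical integration over equicorrelated normal statistics.
- Another marker rises and Ang-2 does not: P(any of four) − 0.025, because Ang-2 alone contributes exactly 0.025. At ρ = 0 this is 0.0963 − 0.025 = 0.0713.

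| ρ | Any of four rises | Another rises, Ang-2 does not | Share of false answers |
|---|---|---|---|
| 0 | 9.6% | 7.1% | 74% |
| 0.5 | 7.8% | 5.3% | 68% |
| 0.9 | 4.7% | 2.2% | 47% |

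**4. With Ang-2 primary at two-sided 0.05 and Holm over the other three**

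- False increase in the primary: 2.5% at any ρ.
- Any false rise in the Holm-adjusted three (simulation): 2.5%, 2.2% and 1.5% at ρ = 0, 0.5 and 0.9.
- Any false rise across primary and secondaries, the like-for-like comparison with 9.6%, 7.8% and 4.7%: about 4.9%, 4.2% and 2.8% (simulation; other runs gave up to 4.3% and 2.9% for the last two). At ρ = 0 this agrees with 1 − 0.975 × 0.975 = 4.9%.

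**5. Alternative: Holm over all four as equals**

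If only Ang-2 rises and its single-test power is 80%, the first Holm step uses 0.0125 two-sided (critical value 2.498). Power at that step is Φ(2.802 − 2.498) = Φ(0.304) = 61.9%. Full Holm by simulation gives about 62% at each of the three correlations.

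**The case against.** **Ang-2 can be inferred.** It is the only increase that Aim 2 reports, and the rationale speaks of a single marker. This stands as far as the sample size goes: a reader might infer that the basis of 78 is unknown or that 78 is too small, and the documents support neither. It does not settle the outcome, because the sentences that define what will be assessed are plural and item 2 lists four.

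**The label may be a drafting slip.** Collective labels are loose throughout, item 1 has a fitting one, and all four markers would be visible in any report. That is fair, and it limits the weight of the label on its own. But the slip, if it is one, sits in the sentence that defines the Aim 3a outcome, and no ranking elsewhere corrects it.

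**The error rates rest on a rule that the plan does not state.** This is true. A reader might infer that the plan will declare success on any of four markers; it does not say so. The rates show what the wording permits. The missing hierarchy needs no such assumption.

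**The gain can be overstated.** Setting 9.6% beside 2.5% compares different events, any marker before and Ang-2 alone after. Like for like, at zero correlation, the change is from 9.6% to about 4.9%.

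**This is a mechanistic study with no treatment decision attached.** That bears on severity. It does not remove the need to say which result would count as validation.

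**Conclusion.** The point holds. Item 2 defines the Aim 3a outcome as four unranked markers under a label that the document's own classes support for Ang-2 only, and nothing in the document ranks them, sets a decision rule or controls multiplicity. The textual finding rests on no assumption.

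Its numerical size does rest on assumptions: an any-marker reading, no true change, and correlations chosen for illustration. Under them the false-increase rate is about two to four times the 2.5% of a single marker, and at correlations of 0 and 0.5 most of those false answers come from a marker other than Ang-2.

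The missing effect size, SD and test behind 78 are missing detail, not evidence of an error. The change should be made, but it is an inexpensive improvement and does not show that the study is mis-sized.

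**What to change.** Before any Aim 3a results are seen:

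- Name the change in serum Ang-2 from baseline to 4 weeks as the single primary outcome of Aim 3a, two-sided 0.05.
- Make SP-D (epithelial), MMP-7 (epithelial and matrix) and osteopontin (fibrogenesis and matrix) secondary under those labels, either with Holm adjustment or as estimates with confidence intervals.
- Correct the label in Outcome measures, item 2, and reconcile the plural endothelial wording in Study Purpose and Rationale, Study Design (revised Aim 3), Selection Criteria, and Research Questions/Hypotheses.
- While editing the sample-size sentence, name Ang-2 and give the effect size, SD of change and test behind 78.
- If any Aim 3a results have already been seen, say so when naming the primary. The documents do not give accrual or assay status.

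The cost is wording only, with no change in sample size, assays or visits. The downside is that a true rise confined to SP-D, MMP-7 or osteopontin becomes secondary evidence. Holm over all four would keep the markers equal and also close the gap, but it would cut power for Ang-2 from 80% to about 62% if only Ang-2 rises.
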